5.6. Subgroup Analyses for Efficacy

To explore the uniformity of the overall treatment effect in subgroups, change from baseline in ALSFRS-R at Week 24 for the subgroups listed below. This analysis will be performed using the MMRM analysis described in Section 5.2, with a treatment by subgroup interaction term added to the model. Subgroups with too few subjects resulting in model non-convergence will be summarized using descriptive summaries of the change from baseline in ALSFRS-R score at week 24.

- Sex (male, female)
- Race (white, non-white)
- Geographic region (North America, Europe, South America, Asia)
- Age at baseline ($<65, \ge 65$ years)
- Slow vital capacity at baseline (<80%, $\ge 80\%$)
- Definite and probable ALS at screening
- Duration of symptoms (<12 months, ≥ 12 months)
- TRICALS Risk Profile (< -4, \ge -4)
- Kings' Stage (1, 2, 3)
- Plasma NfL at baseline (< median value, ≥ median value)
- Decline in ALSFRS-R score during the 8-week screening period (1-2, 2-4, 1-4)
- Use of approved background therapy for ALS (Yes, No)
- Decline in ALSFRS-R score during the 8-week screening period (<4 vs >4) [*]
- Site of ALS onset (limbs, bulbar, other)
- Baseline ALSFRS-R (<41, >=41)
- Family history of ALS (yes, no)

[*] ITT2 analysis set

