1.1. Study Design

Brief description of the Study Design

This is a Phase 2, randomized, double-blind, placebo-controlled, parallel-group study to assess the effects of PTC857 (also known as utreloxastat) in adult male and female subjects diagnosed with ALS. Eligible male and female subjects aged between 18 and 80 years will be enrolled in this study. The study consists of 5 periods: Screening, Treatment (Part A), LTE (Part B), Continued LTE (Part C), and Follow Up as illustrated in Figure 1 below.

Approximately 340 subjects who meet the inclusion and exclusion criteria will be randomized in a 2:1 ratio to receive PTC857 (250 mg BID) or matching placebo with 2 stratification factors:

- 1. Amount of change in ALSFRS-R score during the 8-week Screening Period by points total loss:
 - a. <1,
 - b. 1-2,
 - c. 3-4, or
 - d. >4 points total loss
- 2. Use of edaravone, sodium phenylbutyrate/taurursodiol, or neither for the treatment of ALS at Screening as standard-of-care therapy:
 - e. Edaravone
 - f. Sodium phenylbutyrate/taurursodiol
 - g. Neither edaravone nor sodium phenylbutyrate/taurursodiol

[figure not shown]
Before protocol amendment version 4.0, dated 31 OCTOBER 2022, the second stratification factor above (treatment for ALS at baseline) was based on use of riluzole alone (with two levels: on riluzole and not on riluzole). Protocol amendment 4.0 opened the study to allow for

randomization of subjects who were taking other treatments for ALS, if approved in their region of participation, specifically edaravone or sodium phenylbutyrate/taurursodiol if their treatment was considered stable. In protocol amendment 4.0, the original riluzole stratification groups (on riluzole vs. not on riluzole) would be amalgamated, and randomization would be based on edaravone, sodium phenylbutyrate/taurursodiol, and Neither treatment status, as indicated above.

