5.5.1. Change from Baseline in ALSFRS-R

5.5.1.1. Mixed Model Repeated Measures (MMRM)

Change from baseline in ALSFRS-R at Week 24 will be evaluated by means of a mixed model repeated measures analysis using all available ALSFRS-R scores up to Week 24. The estimand framework described in Section 3.3.2 will be used. The model will include fixed categorical effects of treatment (PTC857 or placebo), use of approved background therapy for ALS (Yes vs No), the amount of change in the subject's ALSFRS-R score during the Screening Period (<1, 1-2 or 3-4 points total loss), time of collection (nominal week at the visit as a categorical variable), as well as the continuous, fixed covariates of baseline ALSFRS-R, and The TRICALS risk profile. In addition, the following interaction terms will be included: Time by treatment, time by baseline ALSFRS-R, and TRICALS risk profile by time. Subject will be included as a random effect. The Restricted Maximum Likelihood (REML) estimation approach will be used with the variance-covariance structure set as unstructured (UN). Other types of covariance matrices will be explored in the case of non-convergence of the UN. Subjects with no post baseline results for the outcome variable will be excluded. This analysis will be performed for both the ITT1 and ITT2 analysis sets.

Observed and change-from-baseline values will also be summarized descriptively at each visit.

In supplementary analyses, score changes from baseline at Week 24 for the ALSFRS-R subdomains will be analyzed under the same estimand framework where MMRM models will be used to implicitly impute missing data. Nominal P-values for the treatment arm comparison, estimate of LSMEANS for the treatment differences (PTC857 – Placebo) at Week 24, and the two-sided 95% confidence intervals of the LSMEANS difference will be presented.

5.5.1.2. Analysis of Covariance Model (ANCOVA) with Multiple Imputation:

An additional analysis to evaluate change from baseline in ALSFRS-R will be performed using an analysis of covariance model (ANCOVA) following multiple imputation (MAR assumption). Missing ALSFRS-R scores, (including those missing due to death) will be imputed using multiple imputation (MI), 100 imputations will be generated using PROC MI in SAS. The Fully Conditional Specification (FCS) model using the regression method will be used.

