14. APPENDIX 4: SAS CODE

Mixed Model Repeated Measure

The following is example SAS syntax for producing least squares estimates, for the MMRM analysis:

```
proc mixed data=ALSFRS_LONG method=reml;
  class ID TRTRND(ref="0") STADCARE(ref="3") CHANGE(ref="<1")
TIME(ref="baseline");
  model DELFRS = TIME VALUEBL CHANGE STADCARE TIME*TRTRND TIME*VALUEBL TRP
  TIME*TRP / ddfm=kr solution;
  repeated TIME / type=UN subject=id;
  lsmeans trtrnd*TIME /cl pdiff=control('0' '5')cl;
  run;</pre>
```

where id is the subject identifier, trtrnd is the randomized treatment arm, stadcare is a factor variable for the SoC stratification group at baseline, change is the amount of change in the subject's ALSFRS-R score during the Screening Period, time is the categorical variable for study visit, Valuebl is the baseline ALSFRS-R score, TRP represents the TRICALS risk profile at baseline, and the response variable DELFRS is the change from baseline in ALSFRS-R score.:

ANCOVA with Multiple Imputation

SAS code for the ALSFRS-R endpoint at 24 weeks:

```
proc mi data = ALSFRS_DATA out = ALSFRS_DATA_OUT
    seed = 20221219 nimpute = 100 noprint;
    class trtrnd stadcare change sex;
    var trtrnd Valuebl change stadcare sex age trp
    ALSFRS_R_4 ALSFRS_R_8 ALSFRS_R_12 ALSFRS_R_16 ALSFRS_R_20 ALSFRS_R_24;
    fcs reg(ALSFRS_R_4 ALSFRS_R_8 ALSFRS_R_12 ALSFRS_R_16 ALSFRS_R_20
    ALSFRS_R_24);
    run;
```

The next set of code performs the analyses for the ALSFRS-R 24-week endpoint:

```
proc reg data=ALSFRS_DATA_OUT utset=outreg covout noprint;
  model ALSFRS_24 = trtrnd Valuebl change stadcare TRP;
  by _Imputation_;
  run;
```

This step will combine the results:

```
proc mianalyze data=outreg;
  modeleffects Intercept trtrnd Valuebl change stadcare TRP;
  run;
```

Pattern Mixture Model

The strategy implemented to carry out the control-based PMM assumes that all other variables, except ALSFRS-R, with missing data are first imputed using the FCS approached outlined in the previous sensitivity analysis, with 100 imputation datasets. These data are stored in DATAIN_IMP0, which contains a variable _Imputation_ to distinguish between multiple copies of the original input data. In the next step missing ALSFRS-R at the first time point will be imputed (the first time-point that has some missing data). To use the control-based imputation

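### SAP 5.6: the subgroup analysis cites the wrong section, its screening-decline groups overlap and omit <1, and its single interaction term should be written as visit-crossed

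*SAP*

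**What the plan says.** Section 5.6 of the Part A SAP sets the Week 24 change in ALSFRS-R as the quantity to compare across subgroups. It then states: "This analysis will be performed using the MMRM analysis described in Section 5.2, with a treatment by subgroup interaction term added to the model". Subgroups too small for the model to converge get "descriptive summaries of the change from baseline in ALSFRS-R score at week 24", so the fallback is also a Week 24 quantity.

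Section 5.2 is a repeat of the primary CAFS ANCOVA without the stratification factors. The ALSFRS-R MMRM is in Section 5.5.1.1, which spells out its crossings with visit: "the following interaction terms will be included: Time by treatment, time by baseline ALSFRS-R, and TRICALS risk profile by time". The Appendix 4 code does the same, in the statement beginning "model DELFRS = TIME VALUEBL CHANGE STADCARE TIME*TRTRND TIME*VALUEBL TRP". Neither place has a subgroup term, and Section 10 puts the table shells in a separate document.

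One ITT1 subgroup line reads "Decline in ALSFRS-R score during the 8-week screening period (1-2, 2-4, 1-4". Randomisation (Section 1.1) used <1, 1-2, 3-4 and a fourth stratum, "d. >4 points total loss". The MMRM in 5.5.1.1 lists this factor with three levels only (<1, 1-2, 3-4), and adds: "This analysis will be performed for both the ITT1 and ITT2 analysis sets".

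**The concern.** Three things in this part of the plan cannot be programmed with confidence.

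- **Groups.** A loss of 2 points falls in all three listed groups, a loss of 1, 3 or 4 falls in two, and 1-4 is the union of the others. They cannot be levels of one interaction factor. The <1 stratum, which holds the slowest progressors at screening, is in none of them.
- **Model term.** The target is a single visit, but the one added term is not crossed with visit. Read literally, it forces the subgroup difference to be the same at Weeks 4, 8, 12, 16, 20 and 24. In a progressive disease, where a difference may build up, that dilutes a Week 24 difference in the analysis meant to look for it.
- **ITT2.** The screening-decline factor as written has no level for the patients who distinguish ITT2 from ITT1.

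**Working it through.** **Design figure.** SAP 1.5 gives 205 and 102 patients, a 2-point difference, SD 5.3, survival of 96.5% and 95%, 2-sided 0.05 and about 85% power. Simulating the joint rank test on these inputs gives 85.6%, so N and SD are sound anchors. The documents state no power for subgroups.

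**What the literal term estimates.** Let d be the subgroup difference in treatment effect at the six visits and V the within-patient covariance. The literal estimate is w'd, with w = V⁻¹1 / (1'V⁻¹1). Adding subgroup x visit alone leaves it unchanged. The documents give neither V nor the shape of d, so both are assumptions, with V scaled to SD 5.3 at Week 24 and t the visit week:

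- random slopes with error SD e: V = (5.3² − e²)/24² · tt' + e²I. With a shared baseline error: (5.3² − 2e²)/24² · tt' + e²I + e²11'
- random walk with error SD e: (5.3² − e²) · min(t,t')/24 + e²I
- compound symmetry: equal variances and equal correlations

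Two cases can be done by hand for linear growth. An error-free random walk puts all weight on Week 4, giving 4/24 = 0.17. Compound symmetry weights visits equally, giving the mean of t/24, which is 14/24 = 0.58.

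Share of the Week 24 subgroup difference recovered, with the SE of the literal term for equal subgroups:

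| Assumed covariance | Linear | Square root | Plateau from Wk 12 | Quadratic | Starts after Wk 12 | Constant | SE |
|---|---|---|---|---|---|---|---|
| Random slopes, e = 1.0 | 0.04 | 0.36 | 0.43 | −0.21 | −0.35 | 1.00 | 0.22 |
| Random slopes, e = 2.5 | 0.22 | 0.48 | 0.56 | −0.01 | −0.13 | 1.00 | 0.47 |
| Same, shared baseline error | 0.26 | 0.51 | 0.60 | 0.05 | −0.07 | 1.00 | 0.75 |
| Random walk, e = 0 | 0.17 | 0.41 | 0.33 | 0.03 | 0.00 | 1.00 | 0.52 |
| Random walk, e = 2.0 | 0.27 | 0.50 | 0.51 | 0.10 | 0.03 | 1.00 | 0.62 |
| Compound symmetry, 0.7 | 0.58 | 0.74 | 0.83 | 0.42 | 0.33 | 1.00 | 1.11 |

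**Example.** Take true Week 24 effects of 1 and 3 points, linear growth and equal subgroups. The literal model reports 2 ∓ share: 1.96 and 2.04 (first row), 1.83 and 2.17 (error-free random walk), or 1.42 and 2.58 (compound symmetry).

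**Simulation.** There were 4,000 datasets per case, with complete data, a re-estimated unstructured covariance, 103+102 active and 51+51 placebo patients, and linear growth.

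| Week 24 subgroup difference | Literal term rejects | Visit-crossed term rejects |
|---|---|---|
| 0 | 5.0-5.9% | 4.4-5.8% |
| 2 points | 7-20% | 33-35% |
| 4 points | 13-55% | 87-89% |

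**Precision of the Week 24 contrast.** For equal subgroups the SE is 5.3 × √(1/103 + 1/102 + 1/51 + 1/51) = 1.28, a half-width of 1.96 × 1.28 = 2.5 points. It is 1.40 for a 30/70 split, 1.61 for 20/80 and 2.14 for 10/90. For ≤4 against >4 in ITT2, 340 − 307 = 33 patients (22 and 11 at 2:1) give 5.3 × √(1/205 + 1/102 + 1/22 + 1/11) = 2.06, a half-width of 4.0 points.

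**Aliasing.** Intercept, a four-level screening factor and treatment have rank 5. Adding a ≤4/>4 main effect leaves rank 5, so that effect is redundant. Adding treatment x subgroup gives rank 6, so the interaction is estimable.

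**The case against.** The strongest reply is that the single term is shorthand. Section 5.6 names Week 24 twice, and in Appendix 4 treatment enters only through its product with visit, with least-squares means by visit. Adding a subgroup to that model plausibly means crossing it with visit, and the shells that would settle it are not available. This stands: the documents show incomplete wording, not a wrong analysis already chosen. A reader might infer that the subgroup results will be wrong; that is not supported.

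A reader might also infer that the literal term routinely reverses the sign of a subgroup difference. It does so only when divergence comes late and the covariance is of random-slope type; random-walk and compound-symmetry cases are zero or positive throughout. For a difference constant from Week 4, the literal term is the better estimator. Section 5.6 promises no interaction p-value or decision rule, so the rejection rates measure sensitivity and do not describe a declared test.

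On the groups, 2-4 may be a slip for 3-4, and 1-4 may be a deliberate pooled group. That would explain the overlap but not the missing <1 stratum.

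On ITT2, a reader might infer that patients with a loss above 4 will be dropped. The documents do not say so. The factor has four levels in Sections 1.1 and 4.2, and in the code it is a class variable, so a >4 value would form its own level unless set to missing. The gap is in the text of 5.5.1.1.

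The ITT2 line "Decline in ALSFRS-R score during the 8-week screening period (<4 vs >4" appears to lose a loss of exactly 4. It is more likely a ≤ sign lost in the text: the ITT1 boundary in Section 2.2 is ≤4, and a sign is also missing from the vital-capacity subgroup in Section 6.9. It needs only confirmation.

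**Conclusion.** The wrong cross-reference, the overlapping groups, the absent <1 stratum and the unwritten >4 level are evident from the text and need no assumptions.

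The loss of sensitivity is conditional on a literal reading that the code leans against. Under that reading, with linear growth, about 4-58% of the Week 24 subgroup difference is recovered. The size rests on assumed covariances and time profiles, a Week 24 SD of 5.3, and complete data. The direction was the same for every growing difference and every covariance tried. Type I error stays near 5%.

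Section 5.6 is exploratory and outside the fixed sequence in Section 4.6, so its model term does not touch the primary or the sequenced secondary results. The ITT2 level is a matter for 5.5.1.1, whose ITT2 analysis is in that sequence, but no bias is shown there. This is a clarification worth making before unblinding. It does not challenge the trial's main conclusions.

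**What to change.** 1. In Section 5.6 cite 5.5.1.1. Include subgroup, subgroup x visit and treatment x subgroup x visit. Report the Week 24 treatment contrast within each subgroup and the Week 24 interaction contrast. Keep the descriptive fallback.
2. In ITT1 use the randomisation strata <1, 1-2 and 3-4, with any pooled 1-4 group as a separate, labelled analysis.
3. In ITT2 models add the >4 level to the screening-decline factor. Where screening decline is itself the subgroup, let the subgroup variable replace that factor, so that main effects are not aliased. Confirm that the ITT2 split reads ≤4 against >4.

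The change is to SAP wording and model terms only. A two-level subgroup needs 12 mean parameters (2 for each of six visits) instead of 2; four-level region needs 36 instead of 6. Non-convergence in small subgroups becomes more likely. Intervals widen: for equal subgroups the SE is 1.28, against 0.22-1.11 for the literal term. If the subgroup difference really is constant over visits, that precision is given up. A 2-point subgroup difference stays underpowered after the change, at about one in three.

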5.7. Overall Survival

Overall survival (OS) is defined as the time in months from the date of first dose to the date of death from any cause or date last known alive for those who did not die.

Specifically,

OS = Date of death or date last known alive – Date of first dose + 1

Subjects will be censored at the last date they are known to be alive. The last known alive date will be the last date of any subject record in the study database. The date may be the last visit date or last contact date that the subject is known to be alive. Subjects who only have baseline record will be censored at the first dose date.

OS will be analyzed using KM methods. A summary table of the number of deaths, the number of censored subjects, and KM estimates (25th, 50th, 75th percentile of OS along with the 95% CI) will be presented. Kaplan-Meier survival curves will also be presented.

A stratified Cox Proportional Hazards regression model will be used to estimate the hazard ratio of PTC857 compared to Placebo. The model will be stratified by the amount of change in the subject's ALSFRS-R score during the Screening Period (<1, 1-2 and 3-4-points total loss), and use of approved background therapy for ALS (Yes vs No). In addition, baseline ALSFRS-R score and the TRICALS risk profile and ALSFRS-R score at baseline will be included in the model as covariates. Ties in survival time will be handled using the Breslow method. Hazard ratio between the treatment groups and the corresponding 95% confidence intervals will be presented.

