At the successful completion of the Treatment Period, all subjects will be offered the opportunity to enter the LTE Period of the study. Those who choose to enter will sign an additional Informed Consent Form (ICF) and continue treatment with PTC857 250 mg BID, as described below. Those who choose not to enter the LTE Period will stop treatment, and a Telephone Follow-Up Visit will be conducted 4 weeks (±3 days) after the last dose of study treatment.

Long-Term Extension Period (Part B)

Subjects who enter the LTE Period of the study will continue treatment for an additional 28 weeks. All subjects will receive open-label PTC857 (250 mg BID) in the LTE Period. Subjects will remain blinded to their original treatment from the Treatment Period (Part A).

Subjects will complete all activities as per the Schedule of Assessments (Table 2). At the end of the LTE Period, those who choose not to enter the Continued LTE Period will stop treatment, and a Telephone Follow-Up Visit will be conducted 4 weeks (± 3 days) after the last dose of study treatment.

Continued Long-Term Extension Period (Part C)

Subjects who enter the Continued LTE Period (Part C) will continue treatment for an additional 108 weeks. All subjects will be treated with open-label PTC857 (250 mg BID) during the Continued LTE Period. Subjects will remain blinded to their original treatment from the Treatment Period (Part A).

Subjects participating in the Continued LTE Period will complete all activities as per the Schedule of Assessments (Table 3). At the end of this period, a Telephone Follow-Up Visit will be conducted 4 weeks $(\pm 3 \text{ days})$ after the last dose of study treatment.

Results from the Treatment Period (Part A), the LTE Period (Part B), and the Continued LTE Period (Part C) will be reported separately.

Pharmacokinetic Sub-Study

Subjects from select sites will participate in the PK Sub-Study. Approximately 36 subjects will take part in an optional PK Sub-Study. These subjects will undergo additional assessments during the study as per the Schedule of Assessments (Table 1).

Table 1: Schedule of Assessments for Screening and Treatment Periods (Part A)

| | | | | | | Treatme | ent Period | | | | EOS/ FU | Early Termination |

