8.4. Statistical Analyses

Detailed methodology for summary and statistical analyses of the data collected in this study will be documented in the SAP. The analysis of the data for the Treatment Period (Part A) (ie, up to the Week 24 Visit) will be produced after the lock of database for Part A. The LTE Period (Part B) of the study will continue for all subjects participating in that part, and results from Part B will be reported separately. The Continued LTE Period (Part C) of the study will continue for all subjects participating in that part, and the results from Part C will also be reported separately.

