1. INTRODUCTION AND OVERVIEW

The purpose of this statistical analysis plan (SAP) is to provide a description of the statistical methods and procedures to be implemented for the analysis of data from PTC857-CNS-001-ALS study, also referred to as The Cardinals Study. This document details the statistical methods to be used in the analyses and presentation of the data collected during the double-blind treatment period (Part A) of the study. The primary efficacy endpoint of the study is assessed during this period.

The statistical methods to be used for the data collected during the entire study including the open-label long-term extension periods (Parts B and C) will be described in a separate SAP.

This document is based on the final protocol amendment version 6.0, dated 14 JUNE 2024, and has been developed, reviewed, and approved prior to the database lock of the double-blind Treatment Period (Part A). Any changes from the planned analysis as described in the protocol for Study PTC857-CNS-001-ALS and its amendments (as applicable) are detailed here, and any differences described here supersede the analysis presented in the protocol. Any additional analyses conducted to supplement the planned analyses and any deviations from the planned analyses described in this SAP will be documented in the Clinical Study Report (CSR).

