3.4. Interim Analysis

No formal interim analyses are planned for this study.

The analysis of the data for the double-blind treatment period (Part A) as outlined in this SAP will be produced after the lock of database for Part A.

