6.2. Adverse Events

Adverse events will be collected and recorded from the time subjects sign the informed consent form to the end of the follow-up period. All AEs will be classified by primary system organ class (SOC) and preferred term (PT) according to MedDRA coding dictionary. A treatment-emergent adverse event (TEAE) is an AE that begins after the first administration of study drug or any existing AEs that worsens after the first dose of study drug. All reported AEs will be listed, but only TEAEs will be summarized in tables.

AEs with an onset from day 1 of the double-blind treatment period up to and including 30 days after the last dose of study drug in the double-blind treatment period (or up to and not including the start date of the LTE period whichever comes first) will be considered as occurring during the double-blind treatment period.

An overall summary of TEAEs presenting number and percentage of subjects reporting at least one TEAE for the categories presented below:

- Subjects with at least one TEAE
- Subjects with at least one TEAE related to study drug
- Subjects with at least one serious TEAE
- Subjects with at least one non-serious TEAE
- Subjects with at least one serious TEAE related to study drug
- Subjects with at least one TEAE leading to premature discontinuation of study drug
- Subjects with at least one TEAE leading to death
- TEAEs by highest relationship to study drug
- TEAEs by highest severity

The following summaries will be tabulated:

- TEAEs overall and by SOC and PT
- TEAEs occurring in \geq 5% of subjects within a treatment group, by PT
- TEAEs by PT
- Study drug related TEAEs, overall and by SOC and PT
- TEAEs by maximum severity, overall and by SOC and PT
- Grade 3 or Higher TEAEs by SOC and PT
- Grade 3 or higher related TEAE by SOC and PT
- TEAEs by highest relationship to study drug
- Serious TEAEs, overall and by SOC and PT
- Serious TEAEs, overall and by severity grade, SOC and PT
- Non-serious TEAEs, overall and by severity grade, SOC and PT
- TEAEs leading to discontinuation of study drug, overall and by SOC and PT
- TEAEs leading to death, overall and by SOC and PT

TEAEs with "possibly related", "probably related" or "related" to study drug based on the investigator assessment will be considered as drug related TEAEs. TEAEs with missing causality, if any, will be assumed as 'Related AEs'.

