3.3. Interim Analysis

No formal interim analyses are planned for this study. However, At the time of the database lock of the double-blind treatment period (Part A) selected data from the open-label long term extension periods (combined Parts B and C) will be descriptively summarized and included in the interim clinical study report. This (select data) will include:

- All available safety endpoints described in Section 6
- All available survival data
- All available ALSFRS-R data
- All available ALSAQ-40 data

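### Part A overall survival has no stop at the end of Part A, contrary to the SAP's double-blind scope, and the sample Cox code does not match the text in either SAP

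*SAP*

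**What the plan says.** **Survival rule.** Part A SAP 5.7 measures overall survival from first dose to death or last known alive, and for the latter says: "The last known alive date will be the last date of any subject record in the study database". No upper limit follows. Estimands 3.3.3 (death) and 3.3.3.1 (death or respiratory support) also run to the event or last follow-up, by randomized arm. Neither lists the start of open-label PTC857 as an intercurrent event.

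**Scope.** Section 1 of the same SAP says methods for "data collected during the entire study including the open-label long-term extension periods (Parts B and C) will be described in a separate SAP". Section 3.4 describes its content as "The analysis of the data for the double-blind treatment period (Part A) as outlined in this SAP". Protocol 8.4 ties this to a visit: "The analysis of the data for the Treatment Period (Part A) (ie, up to the Week 24 Visit". Section 3.2.5 ends the double-blind period at the last Part A dose or the day before the first open-label dose.

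**After Week 24.** Protocol 3.2 states: "All subjects will receive open-label PTC857 (250 mg BID) in the LTE Period". Section 3.3 of the Parts B/C SAP says that at the Part A lock "selected data from the open-label long term extension periods (combined Parts B and C) will be descriptively summarized", and its list includes "All available survival data".

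**Code and time origin.** Appendix 4 of both SAPs describes status as 1 for censored and 0 for death, then codes `status(0)`. Survival starts at randomization in Part A 3.2.13 and Parts B/C 3.2.14, but at first dose in Part A 5.7 and Parts B/C 5.4.

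**The concern.** Survival is a named secondary endpoint, and 5.1 relies on the 5.7 results to describe the survival side of the CAFS result. The ratio is presented as PTC857 against placebo. A programmer following 5.7 alone would take every record in the database. For placebo subjects who entered Part B, that includes time on PTC857. Deaths from a period when both arms take the drug would then enter a comparison labelled as drug against placebo.

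The code matters because it is the only worked specification of the Cox model. If legend and code were both followed, deaths would be censored and survivors would become events. If the MODEL statements were followed, the adjusted model in the text would not be fitted.

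**Working it through.** **1. Passages side by side.** Where the Part A SAP wanted a cut-off, it wrote one. Adverse events in 6.2 run to 30 days after last dose "or up to and not including the start date of the LTE period whichever comes first", and exposure-adjusted rates in 6.2.1 end follow-up within Part A. Section 5.7 and the survival estimands have no such clause. Section 5.4 of the Parts B/C SAP uses the same survival formula and censoring rule for the whole study, so one rule serves two analyses of different scope.

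**2. The plan's own figure.** The planned survival rates enter only the 85% power statement. A joint rank simulation (205 v 102, difference 2 points, SD 5.3, survival 96.5% v 95%, deaths ranked lowest, 20,000 runs) gives 85.4%, so that figure reproduces. No power or event count is stated for survival itself.

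**3. Part A hazard ratio implied by the plan (ITT1).**
- HR = ln(0.965)/ln(0.95) = 0.695.
- Deaths: 205 × 0.035 = 7.2 and 102 × 0.05 = 5.1, total 12.3; survivors 307 − 12.3 = 294.7.
- SE(log HR) = √(1/7.2 + 1/5.1) = 0.58, or 1/√(12.3 × 2/9) = 0.61. The 95% CI is about 0.2 to 2.2.

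**4. Effect of open-label follow-up (illustration).** The documents give neither rollover nor open-label follow-up at the lock. Assumed: rollover fraction f equal in both arms, non-rollovers leaving at Week 24, and the PTC857 hazard in both arms afterwards (open-label HR 1), with weekly hazard h = −ln(0.965)/24 = 0.00148.
- Open-label deaths: E = f × 294.7 × (1 − exp(−h × weeks)).
- Combined HR = exp[12.3 × ln(0.695)/(12.3 + E)].

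| Rollover | Open-label weeks | E | HR | Open-label share of deaths |
|---|---|---|---|---|
| 100% | 13 / 26 / 52 / 78 | 5.6 / 11.2 / 21.9 / 32.2 | 0.78 / 0.83 / 0.88 / 0.90 | 31 / 48 / 64 / 72% |
| 75% | 13 / 26 / 52 / 78 | 4.2 / 8.4 / 16.4 / 24.2 | 0.76 / 0.81 / 0.86 / 0.88 | 26 / 41 / 57 / 66% |
| 50% | 13 / 26 / 52 / 78 | 2.8 / 5.6 / 10.9 / 16.1 | 0.74 / 0.78 / 0.83 / 0.85 | 19 / 31 / 47 / 57% |

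The largest shift is ln(0.904/0.695) = 0.26, which is 0.43 of the Part A SE of 0.61. At 100% rollover the apparent SE, 1/√((12.3 + E) × 2/9), falls from 0.61 to between 0.50 and 0.32. A separate large-sample Cox calculation with 70-90% uptake and 52 to 160 weeks of maximum follow-up gives 0.77 to 0.93, in the same direction.

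**5. Status coding.** `status(0)` makes 0 the censoring value, while the legend makes 0 a death. With a dataset built to the legend and the code run unchanged, about 12 deaths would be censored and about 295 survivors would be events. In a large simulated 24-week sample this turned a ratio of 0.69 into 0.98.

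**6. Cox code against text.**

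| | Text requires | Sample code |
|---|---|---|
| Part A | Stratified by two factors; baseline ALSFRS-R and TRICALS as covariates | STRATA present; TRICALS in CLASS, absent from MODEL, yet a hazard ratio is requested for it |
| Parts B/C | The same | No STRATA; both factors entered as covariates; TRICALS and baseline ALSFRS-R absent from MODEL |

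**The case against.** The strongest reply is that 5.7 should not be read apart from its SAP. Sections 1, 3.2.5 and 3.4 and Protocol 8.4 all point to double-blind data. The Parts B/C SAP assigns open-label survival at the Part A lock to a descriptive summary, and its 5.2 plans the early- versus late-start comparison under its own labels. This stands as evidence of intent. A reader might infer that the sponsor has decided to count open-label time as placebo, and the documents do not support that. They show a rule without a limit that conflicts with general scope statements. The conflict still needs resolving, because 5.7 invokes none of those statements.

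A reader might also infer that the ratio is bound to be pulled toward 1. That depends on a working drug and on hazards becoming similar under open-label treatment, and its size depends on assumed rollover and follow-up. Even the largest illustrated shift is small beside a confidence interval of about 0.2 to 2.2.

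On the code, a reader might conclude that events would be reversed. Part A Appendix 4 calls its survival code sample code, so the text governs. The legend alone may be the slip, and a reversal would show in the table of deaths and censored subjects that 5.7 requires. What stands is that legend and code cannot both be right.

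Nor does the text say that TRICALS is continuous in the Cox model. The reference level in the Part A code and the split at −4 in 5.6 leave a categorical form possible; continuous is inferred from 5.1 and 5.5.1.1.

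**Conclusion.** The point holds as a contradiction in the plan and a risk in its execution. Section 5.7 and both survival estimands lack the Part A limit that the SAP's scope implies. Under the assumptions in the illustration, following them literally would move a planned ratio of 0.69 to about 0.74-0.90 and overstate its precision. The legend conflict and missing Cox terms follow directly from the text of both SAPs. The two time origins are a smaller inconsistency, again in both.

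The reach is limited. Survival is outside the fixed sequence in Part A 4.6, and 5.7 plans an estimate and interval, with no test. The primary analysis and the fixed testing sequence are unaffected by this finding. Severity is minor to should-fix.

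**What to change.** 1. In Part A 5.7, 3.3.3 and 3.3.3.1, state that survival time ends at the earliest of the event, the day before first open-label dose (the boundary in 3.2.5), last known alive, or one common Part A limit. That limit can be the Week 24 visit or, with no such visit, Day 182, the end of its ALSFRS-R analysis window in 4.9. A fixed stop at Day 169 would be worse: visits may fall within ±3 days, so a death in blinded follow-up shortly after Day 169 would be dropped.
2. Count deaths after treatment discontinuation within the limit, in keeping with the treatment-policy strategy. Apply the same limit to deaths in CAFS, so that 5.7 and the result it describes count the same deaths. List later deaths, and leave the early- versus late-start comparison to the Parts B/C SAP.
3. In both SAPs, reconcile the status legend with `status(0)` against the dataset specification, so that deaths are the events.
4. In the Part A code, put TRICALS in MODEL, as continuous unless the SAP defines a categorical form (if continuous, remove it from CLASS), and drop the TRICALS hazard-ratio request. In the Parts B/C code, add STRATA for the two factors and put TRICALS and baseline ALSFRS-R in MODEL, with TRICALS in the same form.
5. Use one survival time origin in both SAPs.

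The cost is SAP and sample-code text. The Part A ratio will rest on about 12 planned deaths and be imprecise. Deaths in non-rollovers between the Week 24 visit and the Day 197 call would be listed only. If Part A hazards continue for those 4 weeks, about 0.5 are expected at 75% rollover: 0.25 × [205 × 0.965 × (1 − 0.965^(4/24)) + 102 × 0.95 × (1 − 0.95^(4/24))]. At 50% rollover the figure is about 1.0.
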